## **4.5 Patient disposition**

The number and percentages of patients allocated to the prednisolone and placebo group will be summarized for all enrolled patients. The number and percentage of patients completing and withdrawing the study, the reasons of withdrawal, and study duration will be reported in a table overall and by treatment.

## **4.6 Demographics and baseline characteristics**

Demographics and baseline characteristics, including birth month and year, sex, smoking , alcohol use, the possession of a smartphone, education level, rheumatoid factor (RF) status, anti-CCP (aCCP) status, duration of RA, evidence of structural joint damage, previous related surgical procedures, previous glucocorticoid use, previous NSAID use, previous DMARD use, previous biological use, number of comorbidities will be reported in a table by treatment group and overall.

## **4.7 Medical history**

Number and percentages of patients with a history of diseases, abnormalities or surgery will be summarized by treatment group and overall. The reported term, preferred term, system organ class, and year of resolution or ongoing will be listed. The MedDRA coding dictionary, version 21.0, will be used to code the medical history.

## 4.8 Benefit analyses

### 4.8.1 Primary analyses

#### 4.8.1.1 DAS28

The following primary benefit hypotheses will be tested for the DAS28 score:

*1a. Primary benefit hypotheses:*

$H_{0,1a}$ : (Null) Prednisolone intake over a period of 24 months leads on average to no difference or a higher score in DAS28 than placebo intake.

$H_{1,1a}$ : (Alternate) Prednisolone intake over a period of 24 months leads on average to a lower score in DAS28 than placebo intake.

$$H_{0,1a}: \mu_T(t = 24) - \mu_C(t = 24) \geq 0$$

$$H_{1,1a}: \mu_T(t = 24) - \mu_C(t = 24) < 0$$

$\mu_T(t = 24)$  is the mean of DAS28 over 24 months in the treatment group.  $\mu_C(t = 24)$  is the mean of DAS28 over 24 months in the control group.

#### 4.8.1.2 Damage score/progression

Damage progression is analyzed as damage at end, with baseline damage as covariate (see model, section 4.10).

The following primary benefit hypothesis will be tested for damage:

*2a. Primary benefit hypothesis:*

$H_{0,2a}$ : (Null) Prednisolone intake over a period of 24 months leads on average to no difference or a higher damage progression compared to placebo intake.

$H_{1,2a}$ : (Alternate) Prednisolone intake over a period of 24 months leads on average to a lower damage progression compared to placebo intake.

$$H_{0,2}: \delta_T(t = 24) - \delta_C(t = 24) \geq 0$$

$$H_{1,2}: \delta_T(t = 24) - \delta_C(t = 24) < 0$$

$\delta_T(t = 24)$  is the mean damage score at 24 months in the treatment group.  $\delta_C(t = 24)$  is the mean damage score at 24 months in the control group.

## 4.8.2 Secondary analyses

The following secondary benefit hypothesis will be tested for the DAS28 in the per-protocol population (see 2.2):

*1b. Secondary benefit hypotheses:*

$H_{0,1b}$ : (Null) Prednisolone intake over a period of 3 months leads on average to no difference or a larger score in DAS28 than placebo intake.

$H_{1,1b}$ : (Alternate) Prednisolone intake over a period of 3 months leads on average to a smaller score in DAS28 than placebo intake.

$$H_{0,1b}: \mu_T(t = 3) - \mu_C(t = 3) \geq 0$$

$$H_{1,1b}: \mu_T(t = 3) - \mu_C(t = 3) < 0$$

## 4.9 Safety analyses

### 4.9.1 Primary analyses

The following primary harm hypothesis will be tested:

*3a. Primary harm null hypothesis:*

$H_{0,3a}$ : (Null) The probability of patients receiving prednisolone to encounter at least one SAE or other AESI (as defined in the protocol) in a period of 24 months is equal to or less than the probability of patients receiving placebo.

$H_{1,3a}$ : (Alternate) The probability of patients receiving prednisolone to encounter at least one SAE or other AESI in a period of 24 months is greater than the probability of patients receiving placebo.

$$H_{0,3a}: \pi_T(t = 24)/\pi_C(t = 24) \leq 1$$

$$H_{1,3a}: \pi_T(t = 24)/\pi_C(t = 24) > 1$$

$\pi_T(t = 24)$  is the probability to encounter an SAE or other AESI over a 24 months period in the treatment group.  $\pi_C(t = 24)$  is the probability to encounter an SAE or other AESI over a 24 months period in the control group.

## 4.10 Modeling and estimating

The testing of the hypothesis sets requires estimating the average effect of treatment on benefit (operationalized as DAS28 and progression of joint damage) and harm (operationalized as encountering at least one SAE or other AESI). An observed effect with a probability of occurrence under the (one-sided) null hypothesis (p-value) of 5% or less will be considered significant causing us to reject the null and to accept the alternative hypothesis. The hypotheses and their tests are one-sided in view of pre-existing knowledge for benefit and the likelihood that true benefit will be underestimated in the context of the pragmatic design and potential differential co-intervention (see section 4.11); and for harm because of limited power. This results in a higher chance of declaring benefit, but also a higher chance of declaring harm.

The average effect of treatment on DAS28 (hypotheses 1) and damage progression (hypothesis 2) will be estimated in a mixed effects regression model. The exact form and empirical fit of the model are important determinants of the power of the statistical test of the treatment effect parameter, as described below. Hypotheses 3 require estimation of the difference in probability to encounter a SAE or other AESI between treatment and placebo over 24 months, which will be implemented by estimating the odds ratio of a SAE or other AESI in treatment versus placebo. All analyses will also take into account that the GLORIA study uses a stratified sampling design, where within each of 28 participating centers randomization is executed stratified by earlier exposure to glucocorticoids (yes/no) and start or switch of other anti-rheumatic drugs at the beginning of the trial.

We first describe how hypothesis testing for the GLORIA study will be executed. In this exposition, we assume that the observed data matrix is complete and that the estimated effects are not confounded with treatment changes. We describe methods to address incomplete data (section 4.2) and to assess confounding with treatment changes (section 4.11).

Our general analysis strategy can be summarized as follows:

1. Test hypotheses 1 to 3 with models described in this section and missing-at-random data correction (section 4.2).
2. Execute robustness checks for monotonous not-missing-at-random data pattern with non-responder imputation (NRI; section 4.2).
3. Assess confounding with treatment changes (section 4.11)
4. Formulate rules to interpret the overall trial results (section 4.12)

### 4.10.1 Model and statistical test for the effect of treatment on DAS28 (Hypotheses 1)

We first consider the analysis of the DAS28 outcome (benefit). The measurement level of DAS28 may be considered continuous so that we can model outcomes by continuous variable models. In the analysis, we need to solve two problems: first, how to estimate an average effect across the study period of two years, and second, how to take the longitudinal data structure into account. The second aspect poses two sub-problems; first, whether to treat time as continuous or discrete and, second, how to take into account that repeated measurements on the same individual are correlated (standard regression techniques assume uncorrelated observations).

The problem of intra-individual correlated observations will be addressed by mixed-effect regression models. The primary distinction in mixed-effect models for longitudinal data is the treatment of time in the model. In so-called fixed-occasion designs, time takes on a discrete form, whereas in so-called variable-occasion designs time takes on a continuous form (Hox, 2010; Snijders & Bosker, 2011). Fixed occasion designs are characterized by the fact that at given occasions outcomes of all (or most) of subjects are observed. Variable occasion designs are not limited by this restriction and there may be a large number of occasions at which only few subjects need to be observed.

Although the design of the GLORIA study in principle lends itself to both types of model classes we will test hypotheses 1 with a fixed occasion model, because the number of time points at which individuals are observed is limited (up to six) and the model can accommodate non-linear trends in the data well by including occasion specific effects and occasion-treatment interactions (see expectations in figure 2). Continuous time models may also accommodate non-linear trends, but then the specification of the functional form becomes crucial and we do not have strong prior expectations of any particular functional model. We note continuous time models may be considered for secondary analyses.

#### 4.10.1.1 Full model

We model the treatment outcome by a mixed effect model with fixed effects measurement occasion after baseline (d), baseline measurement (Z), treatment condition (T), and random effects across individuals (level 2; random intercept U) and study centers (level 3; random intercept V).

Furthermore, we include the strata of the GLORIA trial (S) as fixed effects. Centers could also be modeled as fixed effects, but we have chosen random effects because several centers have included only a very low number of patients. A compound symmetry correlation structure is assumed.

We write down mixed effect model 1 as:

$$\begin{aligned}
 Y_{ijk} &= \beta_{0jk} + \sum_{s=1}^4 \beta_{1jks} d_{ijks} + \epsilon_{ijk} && \text{(level-1 model)} \\
 \beta_{0jk} &= \delta_{00k} + \delta_{01k} S_{jk1} + \delta_{02k} S_{jk2} + \delta_{03k} T_{jk} + \delta_{04k} Z_{jk} + U_{0jk} && \text{(level-2 model for intercept)} \\
 \beta_{1jks} &= \delta_{10ks} && \text{(level-2 model for slope)} \\
 \delta_{00k} &= \gamma_{000} + V_{00k} && \text{(level-3 model for intercept)} \\
 \delta_{01k} &= \gamma_{010} && \text{(level-3 model for slope)} \\
 \delta_{02k} &= \gamma_{020} && \text{(level-3 model for slope)} \\
 \delta_{03k} &= \gamma_{030} && \text{(level-3 model for slope)} \\
 \delta_{04k} &= \gamma_{040} && \text{(level-3 model for slope)} \\
 \delta_{10ks} &= \gamma_{100s} && \text{(level-3 model for slope)}
 \end{aligned}$$

with  $U_{0jk}$  the individual-level random effect,  $V_{00k}$  the center-level random effect, and  $\epsilon_{ijk}$  the residual.

The indices:

- i= 1,..., m : fixed measurement occasion after baseline (in GLORIA, m=5)
- j= 1,...,n : individuals
- k=1,...,K : study centers (currently, K=28 in GLORIA)

The variables:

- $Y_{ijk}$  : DAS28 outcome
- $d_{ijks}$  : dummy variables encoding the five measurement occasions after baseline, s=1,..., 4
- $T_{jk}$  : treatment indicator, 0 if placebo, 1 if active (prednisolone) treatment
- $Z_{jk}$ : Baseline measurement of DAS28
- $S_{jk1}, S_{jk2}$ : Stratification factors

The parameters:

- $\gamma_{000}$ : the model intercept
- $\gamma_{010}$ : fixed effect of stratification factor 1
- $\gamma_{020}$ : fixed effect of stratification factor 2
- $\gamma_{030}$ : fixed effect of treatment
- $\gamma_{040}$ : fixed effect of baseline measurement of DAS28
- $\gamma_{100s}$ : effect of time dummy s

And the random effects :

- $U_{0jk}$  : random intercept of individual i
- $V_{00k}$ : random intercept of study center
- $\epsilon_{ijk}$ : residual

In hypotheses 1, we test for a difference in mean DAS score across a time of 24 months between treatment and placebo. In model (1), this difference in means is estimated by parameter  $\gamma_{030}$ . For the PP analysis at 3 months, the model becomes two-level (no time) as there is only one assessment post baseline.

#### 4.10.1.2 Testing and exploration of treatment-time interactions

The significance of all parameters in model 1 is evaluated using t-tests with Satterthwaite's method for approximating degrees of freedom (Kuznetsova, Brockhoff, and Christensen, 2017). In particular, hypothesis H1a is tested by evaluating the one-sided p-value of  $\gamma_{030}$  rejecting the one-sided null hypotheses if  $\gamma_{030} < 0$  significantly and not rejecting else. The main effect of measurement occasions across all dummy variable d is evaluated jointly by a likelihood ratio test (LRT).

After this assessment, we will explore in a secondary analysis if the interaction between treatment and measurement occasions (time) interaction is significant using a LRT. If this test is significant we will test at which measurement occasions there is a significant difference using t-tests with Bonferroni correction of the p-values.

#### 4.10.2 Model and statistical test for the effect of treatment on damage score (hypothesis 2)

The treatment effect on the damage score at 24 months (hypothesis 2) will be evaluated by the total Sharp/van der Heijde damage score of hands and forefeet. We will use a linear mixed-effects regression model defined similarly to model 1. Contrary to model 1 there are no repeated measurements. Therefore, we model outcomes of individuals nested in centers and include as main effects treatment, design strata, and the baseline measurement of the damage score. A random effect for study center is included. Model 2 is formalized as follows:

$$\begin{aligned}
 Y_{jk} &= \delta_{0k} + \delta_{1k}S_{jk1} + \delta_{2k}S_{jk2} + \delta_{3k}T_{jk} + \delta_{4k}Z_{jk} + U_{jk} && \text{(level-1 model)} \\
 \delta_{0k} &= \gamma_{00} + V_{0k} && \text{(level-2 model for intercept)} \\
 \delta_{1k} &= \gamma_{10} && \text{(level-2 model for slope)} \\
 \delta_{2k} &= \gamma_{20} && \text{(level-2 model for slope)} \\
 \delta_{3k} &= \gamma_{30} && \text{(level-2 model for slope)} \\
 \delta_{4k} &= \gamma_{40} && \text{(level-2 model for slope)}
 \end{aligned}$$

where now  $Y_{jk}$  is the damage score at 24 months and  $Z_{jk}$  is the damage score at baseline. Equivalent to section 3.1.1, it can be see that if a one-sided t-test of  $\gamma_{30} < 0$  is significant,  $H_{0,2}$  is rejected.

We note that the damage progression measurement can be positively skewed, threatening the accuracy (type 1 error rate) of the statistical tests in small samples (and other tests of regression coefficients including t- and F-tests). If we observe a strongly skewed distribution we will apply a bootstrapped test procedure instead of the t-test.

#### 4.10.3 Model and statistical test for the effect of treatment on harm: SAEs or other AESIs (Hypotheses 3)

Contrary to the hypothesis set 1 on the benefit of prednisolone treatment, hypotheses 3 require testing the difference in probabilities of encountering at least one SAE or other AESI over 24 months. On marginal level it would be sufficient to estimate these probabilities after  $t=24$  months and evaluate the significance of their difference. However, to additionally account for the stratification of the GLORIA design, we apply a logistic mixed-effects regression (model 3):

$$P_{jk} = g^{-1}(\delta_{0k} + \delta_{1k}S_{jk1} + \delta_{2k}S_{jk2} + \delta_{3k}T_{jk} + U_{jk})$$

$\delta_{0k} = \gamma_{00} + V_{0k}$	(level-2 model for intercept)
$\delta_{1k} = \gamma_{10}$	(level-2 model for slope)
$\delta_{2k} = \gamma_{20}$	(level-2 model for slope)
$\delta_{3k} = \gamma_{30}$	(level-2 model for slope)
$\delta_{4k} = \gamma_{40}$	(level-2 model for slope)

where now  $P_{jk}$  the probability of patient  $j$  in center  $k$  to encounter at least one SAE or other AESI over 24 months. The function  $g^{-1}$  denotes the inverse of the log link. Significance of  $\delta_{3k}$  will be evaluated with a t-test. Note that model 3 uses the log link as opposed to, for example, the logit link to estimate and test relative risk.

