Damage progression will be evaluated by the change in total Sharp/van der Heijde damage score of hands and forefeet. It is known that this variable has a positively skewed distribution. Cumulative probability plot with the distribution of change in total Sharp/van der Heijde score from baseline to two-year follow-up will be applied as well as a non-parametric test (the Mann-Whitney test) to compare intervention and control groups.

Harm

The primary outcome variable for harm is operationalized as a binary variable with two categories (0= no adverse event, 1= at least one adverse event of special interest (see 9.1.1.a). This variable will be presented as a proportion. A chi-square test will be used to test for differences between the proportion of adverse events in intervention and control groups.

Secondary analyses:

A logistic regression model with harm as dependent variable will be fitted in order to adjust for potential factors that may alter the probability of AEs (as explained above for benefit). In addition absolute incremental risk and relative risk will be calculated for all major events, with confidence intervals.

Analysis strategy:

- One-sided significance levels (alpha=0.05); asymmetric null hypotheses: this approach increases the chance of rejecting the null hypotheses compared to standard two-sided testing. This results in a higher chance of declaring benefit (justified in view of scientific knowledge and the pragmatic trial design), but also a higher chance of declaring harm (to guard against the limited power of the study to detect harm).
 - confirmation of benefit: on the basis of the trial data we expect to reject the null hypothesis of GC (added to standard of care) yielding similar effectiveness compared to placebo (H_0); the alternative (H_1) hypothesis is that GC yields better effectiveness;
 - demonstration of absence of harm: we expect NOT to reject the null hypothesis that GC yields similar side effects; see 4.4 for considerations of the 95% non-inferiority confidence bound.
 - In case the trial detects a difference in AEs favoring the GC group, the superiority of GC will be tested in a secondary analysis.

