## 6 Sample size and power calculations

In the main GLORIA trial, 225 patients per treatment group will be entered (total 450 patients).

In the chosen analysis strategy (see section 4), to detect differences in benefit (disease activity, radiographs) extensive RA trial experience (both for GC and other agents) has shown a sample size of 200 patients per group is amply sufficient. For example, in the CAPRA-2 study that compared modified release prednisone 5mg/d against placebo, the prednisone group had 231 patients, the placebo group 119 patients. The change in DAS28 after 3 months of treatment was  $-1.15$  in the prednisone group,  $-0.63$  in the placebo group; difference  $-0.52$  (SE 0.13,  $p<0.001$ ) (Buttgereit, 2013). However, the true incidence of adverse events (AEs) for GCs is currently unknown. Most relevant data to assess sample size adequacy for this study come from the reported CAMERA-2 trial (Bakker, 2012). This trial randomized 236 early RA patients to tight-control high-dose methotrexate plus 10 mg prednisolone or placebo for two years. Interestingly, 22% of placebo patients compared to only 14% of prednisolone patients reported at least one serious AE or clinical event as defined in our protocol.

The original protocol used a base case expectation for a total of 20% of patients experiencing at least one event over two years in the placebo group and calculated a need for 400 patients in each treatment group, to have about 80% power to detect an increase of 7% (from 20% to 27% events; 90% power for an increase of 9%). However, based on our current experience the sample can be decreased to about 450 instead of 800.

Elaboration:

In December 2018 we had >400 patients in the trial with a mean follow up of 9 months, and we had 84 cases with at least one serious adverse event or an event of special interest (the primary harm outcome). A simple extrapolation leads to an estimated rate of about 49% over 2 years (pooled over the whole blinded trial population, i.e. both treatment groups taken together). We have also performed life table analysis, which accounts for patients stopping prematurely; this analysis leads to an estimated rate of 40% (95% confidence interval: 30%-50%).

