Given the above we can now assume with confidence that the base rate of patients with events in the placebo group will be substantially higher than originally predicted. This adds power to the trial: we need only between 400 and 450 patients to detect the originally targeted contrast of 27.5%/20% = relative risk of 1.38 (Table 1). At the expected pooled event rate of 40%, with 400 patients we have 80% power to detect a difference of 12% between placebo and prednisolone: i.e. placebo 34% and prednisolone 46%, a relative risk of 1.35. The results are better with 450 patients, and when the event rate is higher (Table 1). At the moment of submission of the amendment trial recruitment has been closed on December 31, 2018 at a total of 452 patients.

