**Table 1. Sample size scenarios (one-sided alpha 5%).**

expected event rate over 2 years		with power 80%,			
(% unique patients with at least one event)		detectable rate in predn group		Relative Risk	
pooled	placebo	n=400	n=450	n=400	n=450
30%	26%	38%	37%	1,47	1,43
35%	30%	42%	41%	1,40	1,37
40%	34%	46%	45%	1,35	1,32
45%	39%	52%	52%	1,31	1,31
50%	43%	55%	55%	1,28	1,28

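### The primary harm model leaves out age and comorbidity count; adjusting for them would add a modest amount of power, about 1 to 5 points, if they predict events

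*SAP*

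**What the plan says.** SAP 4.10.3 (model 3) analyses the occurrence of at least one SAE or other AESI over 24 months: "to additionally account for the stratification of the GLORIA design, we apply a logistic mixed-effects regression (model 3"). Its equation contains treatment, two stratification factors and a random centre intercept, with a log link so that the relative risk is estimated and tested. A fifth coefficient (gamma_40) is listed below the equation, but no covariate is attached to it. In model 2 that position belongs to the baseline damage score.

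SAP 4.6 lists birth month and year among the baseline characteristics, and the list ends "previous biological use, number of comorbidities will be reported in a table by treatment group and overall". Neither age nor comorbidity enters a harm model. Protocol 9.2 stratifies the minimisation by site, prior GC exposure and concurrent start of other antirheumatic therapy only.

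SAP 4.10 explains that tests are one-sided for benefit because of prior knowledge "and for harm because of limited power". SAP 6 states that "with 400 patients we have 80% power to detect a difference of 12% between placebo and prednisolone". The rates behind this are 34% in the control arm against 46% in the active arm, a ratio of 1.35. SAP 4.12 counts the absence of a significant increase as harm success. It then grades a non-significant increase by whether the upper one-sided 95% limit is at or below 1.2, between 1.2 and 1.3, or above 1.3.

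Protocol 11.1 makes an unadjusted chi-square test the primary harm analysis. It adds a secondary logistic model "fitted in order to adjust for potential factors that may alter the probability of AEs", and explains these factors by pointing back to the benefit analysis.

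**The concern.** In patients aged 65 and over, age and comorbidity burden are natural candidates for predicting serious events, infections, fractures and cardiovascular events. A harm model without them leaves explainable outcome variation in the error term. In most superiority tests, power left unused works against the sponsor's claim. Here it works in favour of a reassuring conclusion, because non-rejection is the successful result. The plan already accepts a one-sided 5% level to help detect harm; prognostic adjustment can add to that without relaxing alpha further.

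The second issue is chance imbalance. Minimisation did not control either variable, and the grading limits of 1.2 and 1.3 lie close together, so an ordinary imbalance in age or comorbidity could affect which category the result falls in.

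**Working it through.** **Inputs.** Event rates of 34% and 46% with 400 patients (SAP 6). For 450 patients, 34% and 45% (SAP 6, Table 1, headed "Sample size scenarios (one-sided alpha 5"%). Planned size: "225 patients per treatment group will be entered (total 450 patients"). Harm data are taken as complete (SAP 4.2). The documents do not give the prognostic strength of age and comorbidity count, so it is an assumption, shown as a range. Strata and centre effects are left out of all calculations.

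**Step 1: the plan's own figure.** With n per arm and p̄ the mean of the two rates,

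power = Φ{[Δ − 1.645·√(2p̄(1−p̄)/n)] / √[(p_C(1−p_C) + p_T(1−p_T))/n]}.

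- n = 200, 34% vs 46%: (0.12 − 1.645 × 0.04899)/0.04862 = 0.811, so power is 79.1%. The stated 80% reproduces.
- n = 225, 34% vs 45%: (0.11 − 1.645 × 0.04609)/0.04580 = 0.746, so power is 77.2%. The exact detectable rate for 80% is 45.4%, so this gap is rounding in the table.

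**Step 2: analytic gain.** If the covariates explain a share R² of outcome variance, replace n by n/(1 − R²).

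| R² | 400 patients, 34% vs 46% | 450 patients, 34% vs 45% | Effective size for 450 |
|---|---|---|---|
| 0 | 79.1% | 77.2% | 450 |
| 1% | 79.5% | 77.6% | 455 |
| 2% | 79.8% | 78.0% | 459 |
| 5% | 80.9% | 79.1% | 474 |
| 10% | 82.8% | 81.0% | 500 |

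**Step 3: simulated gain.** 225 per arm, 34% vs 45%, one-sided 5%, two independent standardised covariates, 4,000 trials per row. The Monte Carlo SE of each power is about √(0.77 × 0.23/4000) = 0.0067, or 0.7 points. The two blocks are separate runs.

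| Test | OR per SD: age, comorbidity | Without | With |
|---|---|---|---|
| Logistic | 1.2, 1.3 | 77.4% | 78.7% |
| Logistic | 1.35, 1.6 | 77.1% | 78.9% |
| Logistic | 1.5, 2.0 | 77.2% | 82.3% |
| Log link, robust SE | 1.0, 1.0 | 76.4% | 76.7% |
| Log link, robust SE | 1.2, 1.3 (R² 2.2%) | 77.3% | 77.7% |
| Log link, robust SE | 1.3, 1.5 (R² 4.8%) | 76.0% | 78.2% |
| Log link, robust SE | 1.5, 1.8 (R² 9.5%) | 76.8% | 81.3% |

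At the weak end the two runs give 1.3 and 0.4 points, either side of the analytic 0.8 at R² = 2%. At the strong end the gain is 4.5 to 5.1 points. With non-prognostic covariates the change (0.3 points) is within simulation error. With 40% in both arms, the adjusted test rejected in 4.6% to 4.9% of trials, so type I error is held.

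**Step 4: chance imbalance.** The band between the two grading limits is ln(1.3/1.2) = 0.080 wide on the log scale. Over the same odds-ratio range, a one-SD chance imbalance in the two covariates shifts the expected log relative risk by 0.018 to 0.039, that is 0.018/0.080 = 23% to 0.039/0.080 = 49% of the band. A 95th-percentile imbalance shifts it by 0.034 to 0.077.

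**Step 5: can the covariates simply be added to model 3?** Not safely. With these two continuous covariates in a log-link Poisson fit, about 5% (weak) to 97% (strong) of simulated trials had at least one fitted risk above 1. SAP 4.10.3 names no fallback for this or for non-convergence.

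**The case against.** The strongest points on the other side are these.

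- **The plan is internally consistent.** Models 1 and 2 add only the baseline value of their own outcome. An event endpoint has no baseline value, and neither benefit model includes age or comorbidity. This stands: leaving them out of model 3 breaks no rule of the plan.
- **The protocol did not promise this adjustment.** A reader might infer from Protocol 11.1 that the SAP dropped a planned adjustment for age or comorbidity. The documents do not support that. The protocol sentence refers back to benefit, where the named factors are site, prior GC exposure, concurrent start of therapy and the baseline value. The SAP moved adjustment for strata and centre into the primary harm test.
- **The comparison is valid without the covariates.** Randomisation covers chance imbalance within the stated error rate. This stands; the argument is about efficiency and stability, not bias.
- **A missed increase is not simply read as safe.** In a simulation at 225 per arm, 34% vs 45%, about 23% of trials missed significance. About 20 of those 23 points had an upper limit above 1.3, which the plan labels a trend towards greater occurrence; only about 0.7 points fell at or below 1.2. This softens the consequence. The formal harm verdict in SAP 4.12 is still success in all of these trials.
- **The gain is small and rests on assumed odds ratios.** True, and the size is stated accordingly.

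**Conclusion.** The point holds as a modest, low-cost improvement. The primary harm model ignores two scheduled baseline variables that may well predict the endpoint. Using them would raise power by about 1 to 5 points at 225 per arm, under assumed odds ratios per SD of 1.2 to 1.5 for age and 1.3 to 2.0 for comorbidity count. It would make essentially no difference if they are not prognostic. It would also steady an estimate that is to be read against two nearby limits. These figures rest on independent covariates, complete data and no modelling of strata or centre.

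Two stronger readings are tempting. One is that the plan itself calls the harm endpoint underpowered. It does not: it speaks of limited power to justify one-sided testing, and its claim of 80% power with 400 patients reproduces at 79.1%. The other is that the power is given away at no cost. There is a cost: continuous covariates do not sit well under the specified log link, so the estimator has to change. Completeness of the comorbidity count is also not documented; the documents show only that it is scheduled.

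**What to change.** Before unblinding, amend SAP 4.10.3 as follows.

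1. Add age (continuous) and baseline number of comorbidities to the primary harm model, next to the strata and centre.
2. Fit a logistic working model. Average the predicted risks over all patients under each arm, and take their ratio as the standardised (marginal) relative risk.
3. Name this ratio, with a delta-method or bootstrap standard error, as the single estimate and the one-sided test. Its upper limit is the one graded against 1.2 and 1.3.
4. State a simple imputation rule for missing covariate values.
5. Keep the strata-only model as a sensitivity analysis.

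The same edit should settle two loose ends: the unattached gamma_40, and the effect measure, which SAP 4.10 gives as an odds ratio and SAP 4.10.3 as a relative risk.

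The cost is a short SAP paragraph and some programming, with no new data collection. The drawback is that the direct log-link fit is replaced as the primary analysis. If the blind has already been broken, report the adjusted result as a labelled sensitivity analysis instead.
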